### **Abstract**

Preterm births make up 10% of all births in the United States and the cost to care for these infants is approximately 10 times higher than term infants. One of the complications that is common in preterm infants is hypothermia. Hypothermia which has been linked to an increased risk of mortality, leads to low glucose, apnea and respiratory distress in preterm infants amongst other complications. Currently, after preterm babies are born we keep them connected to the mother via the umbilical cord for at least 60 seconds because it reduces the risk of complications for the neonate, however, this allows for a significant period of time during which hypothermia may develop. We are proposing a pilot randomized controlled trial evaluating the benefit of immediately warming preterm babies using a warming mattress and a plastic wrap, while we delay clamping the umbilical cord at the time of c-section in babies born between 32 and 36 weeks to determine if it reduces the risk of hypothermia

#### **A. Specific Aims**

We *hypothesize* that neonates delivered preterm and wrapped with a sterile polyethylene wrap while being warmed with a standard neonatal transport warming mattress immediately after birth and awaiting delayed cord clamping will be less likely to be hypothermic at arrival to the neonatal warmer. Since this is not currently a method that is employed, we have insufficient preliminary data to determine a sufficient sample size needed for a randomized controlled trial. **The aim of this grant is to perform a pilot trial investigating the effect size of immediate neonatal warming and wrapping of preterm infants on neonatal temperature.** Our team is well positioned to address these questions as there is tremendous synergy between the maternal fetal medicine and neonatology groups at OU, and our large referral base for preterm deliveries—we accept 600 maternal transfers yearly.

We propose a pragmatic randomized pilot trial evaluating the effect size of this strategy employed for moderate and late preterm infants (32 weeks 0 days to 36 weeks 6 days) who are being delivered by non-emergent cesarean. We plan on enrolling 74 patients and allocating patients to the intervention and control groups 1:1 using a block randomization scheme stratified by gestational age. Patients and clinicians cannot be practically blinded to the interventions given the physical nature of the interventions; however, statisticians will be blinded to the group assignments. Primary outcome will be the difference in temperature of the neonate at time of arrival to the warmer for neonatal evaluation between groups. Secondary outcomes will include temperature at completion of resuscitation, need for NICU admission, temperature upon leaving the delivery room, temperature upon admission to the NICU (if required), hypoglycemia (less than 30mg/dL in the first 24 hours), highest bilirubin level, respiratory support in the form of intubation or continuous positive airway pressure, pulmonary hemorrhage, hyperthermia ( $>37.5$

degrees C), days in the NICU, and composite neonatal morbidity and mortality outcome of death or intraventricular hemorrhage (all grades), sepsis (determined by treating neonatologist). Data obtained from this pilot trial will be used to apply for a NIH K08 grant in order to perform an adequately powered multi-center randomized controlled trial in order to investigate the efficacy of this approach and associated outcomes.

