**E. Chart Review**

All outcomes will be recorded in a REDCap database by research nurses and data managers on the OUHSC campus in prospective fashion. Data will be obtained from maternal and neonatal electronic medical records and only de-identified data will be analyzed from the REDCap database. The primary outcome will be the proportion of hypothermic newborns. Secondary outcomes will include temperature at completion of resuscitation, need for NICU admission, temperature upon leaving the delivery room, temperature upon admission to the NICU (if required), hypoglycemia (less than 30mg/dL in the first 24 hours), highest bilirubin level, maximal respiratory support and duration of respiratory support including but not limited to supplemental oxygen and mechanical ventilation, pulmonary hemorrhage, hyperthermia (>37.5 degrees C), days in the NICU, and composite neonatal morbidity and mortality outcome inclusive of 1) death, 2) intraventricular hemorrhage (all grades), 3) sepsis (determined by treating neonatologist) and 4) Necrotizing enterocolitis. Confounders that will be assessed will include delivery room temperature as reported on the room thermostat, maternal temperature as recorded by anesthesia at the time of delivery, time from delivery to arrival at the neonatal warmer, indication for delivery, indication for cesarean, infant weight, timing of betamethasone administration (time for administration to delivery) and gestational age. Access to the database will be controlled and logged using REDCap's internal systems. Finally, at the completion of the study, the data will be stored for 7 years in order to complete analysis and apply for additional grants prior to being destroyed.

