#### **J. Statistical Methods**

Since this intervention has not been studied previously and requires cohesion between pediatricians and obstetricians, we will plan on hosting in-person and virtual training for key study personnel. Currently, at OU we deliver approximately 250 neonates between 32 and 36 weeks gestation via cesarean each year. Assuming a 33% rate of enrollment, it would take us approximately 11 months to enroll our target sample size of 74 patients.

Two prior studies, one evaluating epidemiology and the other an intervention, demonstrated that 29% of neonates born in the late preterm period were hypothermic in the delivery room with a standard deviation of 8.8. With the proposed enrollment of 74 preterm infants that meet inclusion criteria, we would have approximately 80% power to detect a difference between the two groups of 20%. Since this intervention has not been evaluated previously and we are using indirect data from other institutions and other interventions, we are assuming a 10% increase in sample size (calculated at 68) to account for variations (total of 74). This is a pilot trial to generate the parameters needed to guide the development of the next-step full-scale multicenter trial. Thus, power calculations for the efficacy of the intervention were completed to ensure we did not need to start with a larger or smaller sample size, given the pilot nature of the project.

For this pilot trial, the baseline characteristics of patients assigned to the intervention and control groups will be estimated and compared as means, medians or proportions, as appropriate for the distribution of the data. Descriptive statistics (i.e., proportions, 95% confidence intervals, means, standard deviation, medians, and interquartile range) will be used to characterize the distribution of the primary and secondary outcome measures among the intervention and control groups. Using an intent-to-treat approach, the primary and secondary outcomes will be compared between treatment groups using Student's t-tests, Wilcoxon rank sum tests, chi-square tests or Fisher's exact tests, as appropriate for the variable distributions.

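### Sections A and E name two different primary outcomes (mean arrival temperature and proportion hypothermic), and the hypothermia outcome has no cut-off

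*Combined protocol and SAP*

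**What the plan says.** - Section A, Specific Aims, names a continuous primary outcome: "Primary outcome will be the difference in temperature of the neonate at time of arrival to the warmer for neonatal evaluation between groups".
- Section E, Chart Review, names a binary one: "The primary outcome will be the proportion of hypothermic newborns". That sentence gives no time point and no temperature cut-off. The same paragraph does give limits for other outcomes, for example "hyperthermia (>37.5 degrees C), days in the NICU", and 30 mg/dL for hypoglycemia.
- Section A is itself mixed. Its hypothesis is binary (infants "will be less likely to be hypothermic at arrival to the neonatal warmer"), which at least supplies a time point. Its aim is continuous ("investigating the effect size of immediate neonatal warming and wrapping of preterm infants on neonatal temperature"). The Abstract speaks of hypothermia risk.
- Section J, Statistical Methods, builds its power statement on "29% of neonates born in the late preterm period were hypothermic in the delivery room with a standard deviation of 8.8" and claims "approximately 80% power to detect a difference between the two groups of 20" per cent. It then says that "the primary and secondary outcomes will be compared between treatment groups using" a list of continuous and categorical tests, chosen by the distribution of the variable. It does not say which outcome is primary.
- Two hypothermia temperatures appear in Section B: 36.5 C as the reference for a mortality association, and below 36 C labelled moderate hypothermia. Neither is adopted as the trial's definition.

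**The concern.** A randomized trial that makes a power claim and tests between groups needs one primary outcome fixed before the data are seen. Here two current sections give different ones. They come from the same thermometer reading but are different quantities: a mean difference in degrees C and a difference in proportions. They use different tests and can differ in power, so one may be significant when the other is not. As written, whichever gives the better result could be reported as primary and still be consistent with some part of the protocol.

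The binary version has a second degree of freedom, because the cut-off could also be chosen late. The pilot is meant to supply parameters for a multicenter trial, so the text also leaves open which effect size that trial should be designed around.

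**Working it through.** **1. Does the sample size reveal the intended outcome?** Section J gives 29% hypothermic, SD 8.8 (no unit), a difference of 20%, about 80% power, 68 raised to 74. It states no alpha; two-sided 0.05 is assumed unless noted.

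- *As proportions, 29% vs 9%* (pooled mean 0.19): n per arm = [1.96·√(2·0.19·0.81) + 0.842·√(0.29·0.71 + 0.09·0.91)]² / 0.20² = (1.087 + 0.452)² / 0.04 ≈ 59.2, so 60 per arm, 120 in total (138 with continuity correction). Power is 55.8% with 68 and 59.5% with 74. The figure 68 appears only at one-sided alpha 0.10 without continuity correction, which the plan does not state.
- *As means*, treating 29 as a mean and 20% as relative (0.20 × 29 = 5.8): n per arm = 2·(1.96 + 0.842)²·8.8² / 5.8² ≈ 36.1, so 37 per arm, 74 in total. This gives 74 directly but not 68 (power 77.6%), and it treats a percentage as a mean.
- *Other readings:* an absolute difference of 20 with SD 8.8 gives 8 in total; a 20% relative reduction in the proportion (29% to 23.2%) gives 1,798.

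No reading at two-sided 0.05 yields the 68/74 pair, so the calculation does not identify the primary outcome.

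**2. How far apart are the two outcomes?** Assume normal temperatures, equal SDs, a pure mean shift, 37 per arm, and 29% vs 9% below the cut-off.

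- Implied shift: z(0.29) − z(0.09) = −0.553 + 1.341 ≈ 0.787 SD.
- t-test: noncentrality 0.787·√(37/2) ≈ 3.39 on 72 df; power 91.6%.
- Proportion, exact binomial: chi-square 61.4%, Fisher 50.6%.
- Joint behaviour in 400,000 simulated trials: t-test and chi-square disagree on significance in 32.2% (t-test alone significant 31.2%, chi-square alone 1.0%). t-test and Fisher disagree in 42.1%. Significant results in opposite directions never occurred.

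**3. False positives if either outcome may be claimed.** With no true effect (400,000 simulated trials), at least one is significant in 8.0% with chi-square and 6.4% with Fisher, against a nominal 5%.

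**4. Effect of the missing cut-off.** Keep the 0.787 SD shift and move the cut-off. The 10% and 50% control rates are illustrative, not from the documents.

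| Controls below cut-off | Intervention below cut-off | Chi-square power | Fisher power |
|---|---|---|---|
| 10% | 1.9% | 31% | 9% |
| 29% | 9% | 61% | 51% |
| 50% | 21.6% | 73% | 65% |

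**5. What 37 per arm can detect on temperature.** At 80% power: (1.96 + 0.842)·√(2/37) ≈ 0.651 SD by normal approximation, 0.660 SD by noncentral t. The documents give no usable SD in degrees C. For an assumed SD of 0.4 to 0.8 C this is 0.660 × 0.4 ≈ 0.26 C to 0.660 × 0.8 ≈ 0.53 C.

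**The case against.** The best defence is that this is a pilot and both outcomes come from one reading taken on every infant. Section J plans means, SDs, proportions and confidence intervals, so both effect sizes could be reported once a cut-off is set. The two analyses should agree in direction, and the statisticians are blinded to group. Under the assumed effect, picking whichever test succeeds adds little to the t-test alone: 91.6% + 1.0% = 92.6%. The power gap is also model-based. If wrapping mainly protects the coldest infants rather than shifting the whole distribution, the gap would differ. Section J does not say whether its 20% is absolute or relative. With a pooled expected count of about 0.19 × 37 = 7 hypothermic infants per arm, chi-square is the usual test, so the Fisher figures are the less favourable case. Finally, tests are assigned by variable type, so naming the outcome would largely fix the test.

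Most of this is fair and limits how the numbers should be read. It does not remove the contradiction. Blinding to group does not prevent choosing the outcome with the smaller p-value. Reporting both effect sizes does not say which one decides the trial, and the proportion cannot be derived without a cut-off that the plan does not give. The inflation to 6.4–8.0% is modest, but avoidable.

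**Conclusion.** The concern holds and should be corrected before outcome data are examined by group. The contradiction, and the absence of a hypothermia definition for the trial, are plain from the text and need no calculation.

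The calculations show only that the choice matters. They rest on the stated model (normal, equal SDs, pure shift), on a two-sided 0.05 level that the plan does not state, and on reading Section J's 20% as an absolute reduction. On those terms, power differs by about 30 points with chi-square (91.6 − 61.4) and 41 with Fisher (91.6 − 50.6). The risk is of disagreement on significance, not of opposite findings.

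**What to change.** Name one primary outcome in identical words in Sections A, E and J, with its time point and test, and list the other as secondary.

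- **Suggested, with the choice left to the investigators:** axillary temperature at arrival to the warmer, compared as a mean difference with a 95% confidence interval. It matches the stated aim and keeps more information. The proportion hypothermic at arrival becomes secondary, with one pre-specified cut-off. Because a mean can also rise through overheating, report it beside the planned hyperthermia rate. Restate the power in degrees C, using the 0.66 SD detectable difference and a sourced or openly assumed SD.
- **If the proportion stays primary:** state the cut-off and time point, say that the 20% is absolute if that is meant, and give the actual power at 37 per arm for 29% vs 9%: about 60% by the usual formula (61% exact) for chi-square, or 51% for Fisher. Reaching 80% needs about 60 per arm (69 with continuity correction).

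The cost is wording in three sections plus one new input, a temperature SD in degrees C. The suggested choice has a drawback: the hypothesis and Abstract are framed as hypothermia risk, and that clinically familiar proportion would become secondary.

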## B. **Background and Significance**

Preterm delivery is a significant public health issue, with approximately 10% of births in the United States occurring prior to 37 weeks of gestation, and is a leading cause of perinatal mortality and childhood morbidity. In Oklahoma, 144 babies are born preterm on a weekly basis, representing an average of 11.1% of births in 2017. Although infants born less than 28 weeks are at highest risk for morbidity and mortality, approximately 80% of infants born preterm are born between 32-36-weeks gestation representing the largest proportion of affected neonates. Apart from mortality, these children are at risk for complications that impact multiple organ systems including sepsis, intraventricular hemorrhage, retinopathy of prematurity and respiratory distress. An initial step in improving outcomes according to neonatal resuscitation algorithms includes drying infants and maintaining euthermia, as hypothermia has been associated with an increase in mortality of 28% for each 1C below 36.5 degree C. Such measures are significant as the current rate of mortality ranges from 70% in those born at 23 weeks to less than 1% at 37 weeks, with an even higher proportion suffering from long term morbidity.

Recent recommendations from the American Academy of Pediatrics (AAP) and American College of Obstetricians and Gynecologists (ACOG) recommend delayed clamping of the umbilical cord by 30-60 seconds to minimize severe complications such as intraventricular hemorrhage, necrotizing enterocolitis, and anemia in preterm infants. During this period, the infant remains at risk of hypothermia as heat loss starts immediately after delivery. The infant moves from an environment of the 37°C womb to the temperature in the delivery room, with decreases in temperature between 0.2-1 degree every minute. With the above recommended interventions, the neonate typically does not arrive at the radiant warmer for assessment by the neonatology team until 2-3 minutes of life. Prior studies have investigated warming the neonate using transport mattresses and polyethylene wraps after evaluation by the neonatology team and demonstrated efficacy in minimizing hypothermia at admission to the NICU. There are no contemporary studies evaluating strategies to maintain infant euthermia during delayed cord clamping. As such, there remains a critical gap during which hypothermia may develop and adversely affect the neonatal transition to extrauterine life.

### Preterm delivery and resuscitation in the late preterm period

As a result of the significant physiologic changes that occur postnatally and the risks of morbidity and mortality outlined earlier, strategies to optimize the neonate's transition to extrauterine life have been developed. The first intervention for any preterm neonate consists of delivery at a hospital where neonatal needs are matched by available services. Previous studies indicating that post-natal transfer may increase the risk of neurological dysfunction and death. In addition to expedient maternal transfer, obstetricians administer betamethasone prior to delivery and delay cord clamping after delivery to minimize respiratory distress, intraventricular hemorrhage, minimize the risk of anemia and mortality. Further, there may be an improvement in long term respiratory and neurodevelopmental outcomes, and short term cardiovascular function after delayed cord clamping. Interestingly, the infant is not attended by a

neonatologist during this period of delayed cord clamping. Prior to the recommendation for universal delayed cord clamping in 2017, this period had been acknowledged as the “golden minute” during which neonatologists assessed the infant’s resuscitation needs starting with a maintenance of euthermia, followed by optimization of airway, breathing and circulation over the ensuing ‘golden hour’. While obstetricians stimulate babies, attempt to clear the airway with bulb suction and dry the infant, these measures are executed with significant heterogeneity and variable efficacy. To this end, efforts are underway to investigate the utility of initiating positive pressure ventilation before cord clamping. Such efforts emphasize the perceived importance of the first minutes after birth, since these interventions can improve transition to post-natal life and reduce the risk of morbidity and mortality.

### Hypothermia and Neonatal outcomes

An important component of care in the first few minutes of life, especially in the preterm neonate is ensuring euthermia. Neonates have decreases in their body temperature of 0.2-1 degrees per minute after birth. Preterm neonates are at increased risk for hypothermia due to their increased body surface to weight ratios, thin skin and lower amounts of insulating subcutaneous fat, thus resulting in increased evaporative heat losses. Hypothermia results in increased metabolic and oxygen demands and impaired resuscitation. From an outcome perspective, hypothermic neonates are at an increased risk for respiratory distress, chronic lung disease, metabolic derangements such as hypoglycemia, intraventricular hemorrhage, and late onset sepsis. Even moderate hypothermia (<36 degrees C) has been linked to mortality. De Almeida et al noted that 44% of preterm neonates admitted to one of 12 university hospitals were hypothermic at 5 minutes of life, with 51% experiencing hypothermia at NICU admission. As such, various interventions have been studied during the golden hour and at the time of neonatal transport to the NICU. These include using polyethylene wraps and caps, warming mattresses, warmed humidified gases and maintaining delivery room temperatures at 24 degrees C. Though such interventions may result in hyperthermia (>37.5 degrees C), no correlation between iatrogenic hyperthermia and adverse neonatal outcomes has been demonstrated. However, strategies to avoid hypothermia reduce the need for respiratory support and lower the risk of pulmonary hemorrhage. Thus, beginning to prevent hypothermia during delayed cord clamping presents itself as an opportunity for improvement in outcomes.

### **C. Preliminary Studies/Progress Report**

This proposal includes two Co-PIs, both of whom currently work synergistically within the healthcare delivery system. The question to be addressed is at the transition of life which represents a strength for both PIs as we and our divisions currently collaborate in the care for these patients on a daily basis. The two divisions meet at least twice a month to discuss care related to fetuses and neonates with complex congenital anomalies that require a synergistic and longitudinal approach to care from the womb to the mother’s arms. Individually, each PI will be responsible for ensuring that we lend both of our expertise to the design and execution of this proposal. Troubleshooting concerns and ensuring that stakeholders in each department are invited for and complete training in the study methodology will be an individual mandate for each PI. However, these training sessions, enrollment and data acquisition will be collaborative. Finally, it was via a collaborative effort that we were able to generate a grant application and obtain funding.

### **D. Research Design and Methods (What, When, How, Where)**

### Recruitment

The trial will be advertised and introduced to patients admitted to the OU Children's Hospital labor and delivery or antepartum units by research nurses. Interested participants will be consented. We are choosing to only include patients undergoing non-emergent cesarean in order to improve our ability to control parameters such as room temperature and labor-related clinical or subclinical maternal infection, which are known confounders. Further, we are limiting our investigation to fetuses 32-36 weeks gestation, since this population represents the largest preterm delivery population. Recruitment and randomization will be stratified by gestational age with an aim to enroll at least 44 pregnancies at 32- 34 weeks and 6 days and 20 pregnancies between 35- 36 weeks and 6 days. Last, it is impossible to recruit patients outside of the inpatient setting for a study investigating preterm delivery, as such deliveries are rarely predictable in the outpatient setting. There will only be one site for this study, the OU Children's Hospital labor and delivery and antepartum units.

